1.2.1.2. Safety Pharmacology

The effect of RZL-012 on the central and peripheral nervous systems was evaluated using the Functional Observational Battery (FOB) in male Sprague Dawley rats. RZL-012 was administered subcutaneously to rats (n = 8/group) as 10 mg/rat. From the results, it was concluded that RZL-012 did not affect any of the central nervous system (CNS) functions tested using FOB in rats.

RZL-012-SMF-P2US-001

Version: 1.2

The effect of RZL-012 was evaluated on respiratory functions in male Sprague Dawley rats using head-out plethysmography. RZL-012 was administered subcutaneously at a fixed dose of 10 recorded to cover the entire predetermined time points: Pre-dose, 1, 2, 3, and 4 h post dose. RZL-012 did not affect any of the parameters tested; hence it was concluded that RZL-012 has no effects on the respiratory system at the tested dose of 10 mg/rat.

A board-certified veterinary cardiologist conducted a qualitative and quantitative review of the electrocardiograms (ECGs) obtained pretest, pre-dose, 4 and 24 hours post-dose following the subcutaneous injection of 500 mg 5.0 % RZL-012 or vehicle in Domestic Yorkshire Crossbred Swine. There was no effect of the subcutaneous injection of 5.0% RZL-012 on qualitative or quantitative ECG parameters or blood pressure.

1.2.2. Toxicology

The study design was to evaluate the safety of RZL-012 according to Food and Drug Administration (FDA) guidelines for Exploratory Investigational New Drug (IND) appropriate for first-in-man clinical trial. An extended single-dose toxicity study was performed according to FDA guidance in two species (rat and pig) to establish the NOAEL.

1.2.2.1. Extended Single Dose Toxicity Studies

1.2.2.1.1. Rats

Single subcutaneous administration of test item RZL-012 at the doses of 5, 10, and 20 mg/kg in Sprague-Dawley rats resulted in non-systemic effects and or local effects at the treated skin area. Few changes observed in haematological parameters (changes in white blood cells [WBC] count, neutrophils, monocytes and eosinophils) were considered secondary effects due to inflammatory response (local skin reactions). The changes observed in clinical chemistry parameters (increased blood urea nitrogen [BUN] in males and females and increased creatinine and aspartate aminotransferase [AST] levels in females) at all the doses tested and histopathological changes in kidneys (necrosis in tubular epithelium) at 20 mg/kg were considered systemic effects. Methods and results from the extended single dose toxicity study are described in the Investigator's Brochure (IB).

Considering skin changes as non-systemic effects and or local effects, the NOAEL was determined at 5 mg/rat (approximately 20 mg/kg) under the test conditions and doses employed.

RZL-012-SMF-P2US-001 Version: 1.2

1.2.2.1.2. Pigs

This study was conducted to evaluate the potential local and systemic toxicity as well as efficacy of the test article, RZL-012 (50 mg/mL), in domestic Yorkshire crossbred swine following subcutaneous injection into the subcutaneous abdominal fat on Day 0. Methods and results from the extended single dose toxicity in pigs study are described in detail in the IB.

Assessment of toxicity was based on mortality, clinical observations, body weight, qualitative food consumption, body temperature, subcutaneous fat temperature, blood pressure, physical and electrocardiographic examinations, and anatomic and clinical pathology. Blood samples were collected and analyzed for porcine stress syndrome testing and toxicokinetic assessment of the test article.

Administration of the test article was not associated with any mortality, clinical observations (with the exception of transient redness and swelling at injection sites), body weight or food consumption changes, effects on electrocardiographic endpoints, or changes in clinical chemistry or coagulation parameters.

1.2.3. Additional Nonclinical Studies

- Secondary pharmacology
- ADME-Toxicology study: Establishing pharmacokinetic (PK) parameters, absorption, distribution and metabolism and excretion
- RZL-012 genotoxicity (in-vitro and in-vivo)
- Absorption studies in rats and pigs

Methods and results from these safety studies are described in the Investigator's Brochure.

1.2.4. Clinical Studies

RZL-012 has been tested in several clinical trials. A total of 54 subjects were exposed to RZL-012 at single doses of up to 180 mg. The currently planned clinical trial will be the first trial to test a single maximal dose of RZL-012 of up to 240 mg, (the NOAEL) and the first trial to assess the potential efficacy of RZL-012 in reducing submental fat.

Two studies were completed and one study is still on-going.

Version: 1.1

Table 1: Overview of Ongoing and Completed Clinical Studies

Study ID STATUS	Phase	Country	Study Title	Study Design	Dosing Regimen	Study Population
RZL-012-P0US- 001.3	0	USA	Phase 0 Study of Three Cohorts Aiming at the Evaluation of Safety and Thermogenesis-induction of Three Escalating Doses of RZL-012 Drug Product in Overweight, Healthy Volunteers	A randomized, double-blind, vehicle-controlled, dose-escalation study that will enroll 8 subjects, 6 active and 2 control, in each of 3 cohorts.	Cohort 1: 5 mg Cohort 2: 10 mg Cohort 3: 20 mg	Healthy, 20-40 years old, overweight by Body Mass Index (BMI) definition (25 < BMI ≤ 34.9), adult males.
RZL-012- P2aUS-001.4 COMPLETED	2A	USA	A Double Blind, Randomized, Placebo Controlled, Dose Escalation Phase 2a Clinical Trial for the Evaluation of Safety and Thermogenesis-induction of RZL-012 in Overweight and Obese Volunteers	A randomized, double-blind, placebo-controlled, consecutive 4 cohort, dose escalation clinical trial	Cohort 1: 40 mg Cohort 2: 80 mg Cohort 3: 120 mg Cohort 4: 180 mg	Adult male subjects 20–60 years old, with 27.5 < BMI ≤ 34.9
RZL-012-FD- P2aUS-001.7 ON GOING	2A	USA	An Open Label, Phase 2a Clinical Trial for the Evaluation of Safety and Efficacy of RZL-012 for the Treatment of Women with Lipedema Involving Substantial Fat above the Knee or of Women and Men with Nodular Dercum's Disease	Open-label safety and efficacy clinical trial	Cohort 1 DD: Subjects will receive up to 40 mg RZL- 012 Cohort 2 Lipedema: Each 3 subjects will receive 60 mg or 80 mg RZL-012	Post-menopausal (at least 2 years) women no more than 65 years old, with lipedema involving substantial fat above the knee or nodular Dercum's disease in such women and in men 20–65 years with nodular Dercum's disease

1.2.4.1.1. Protocol No. RZL-012-P0US-001.3. Status: Completed

The first-in-man clinical trial was an exploratory, randomized, double-blind, vehicle-controlled Phase 0 study, conducted under IND 119941 to evaluate the safety and thermogenesis-induction of three escalating doses of RZL-012 in overweight and obese subjects. This study also evaluated the RZL-012 pharmacokinetics at the baseline visit till the following day (Day 0-1).

The primary objective of the study was the evaluation of the overall safety of RZL-012 after subcutaneous injection and the existence of a thermogenic effect. A thermogenic effect was defined by an increase of 1 $^{\circ}$ C in the injected site when compared to the surroundings and/or the contra-lateral (non-injected site), apparent at least 28 days after injection. This was monitored by sensitive (\pm 0.1 $^{\circ}$ C) Infra-Red thermal camera.

The secondary objective was the determination of RZL-012 pharmacodynamics. The evaluation of the extent, duration and tissue associated changes of the thermogenic response to RZL-012, via minimal invasive means including injected-site thermogenesis imaging, Magnetic Resonance Imaging (MRI) and punch biopsy following injection into the subcutaneous fat are summarized below

The study was composed of 3 cohorts where in each cohort 8 subjects were injected (6 active and 2 control). This was a dose escalation study, therefore RZL-012 was injected at doses of 5, 10, and 20 mg/subject at cohorts 1, 2, 3, respectively.

Subjects received a single treatment in multiple sites (1-4) of injection diagonally (45°) to the skin surface at 3 cm lateral to the umbilicus lateral wall. The distance between injected sites was 1 cm (see Figure 1).

Figure 1: Injection Sites for Phase 0 Study

RZL-012-P0US-001.3 Study Results:

RZL-012 was generally found to be safe in all cohorts. There were no clinically significant changes in vital signs, ECG and almost all blood laboratory tests. Most AEs associated with RZL-012 injection were confined to the injection site and were transient. Biopsy from the injection site revealed no damage to the skin 56 days following RZL-012 injection. The only

significant local AE was an abscess in one subject in the lower abdomen at the surrounding of injected side (but away from the injected site).

One systemic clinically significant AE involved a severe elevation of ALT blood levels and a moderate elevation of AST blood levels 17 days following injection of the highest dose (AST 169 U/L; ALT 411 U/L) of active treatment. This elevation was transient. Resolution for AST elevated levels and reduction for ALT levels to Grade 1 according to MeDRA coding dictionary occurred 11 days following detection. ALT levels were normal on the next visit on Day 56. There were no other systemic clinically significant AEs.

PK profile results demonstrated an association between dose and C_{max} with values of 13.11 ng/mL at the lower dose level (Cohort 1), 23.02 ng/mL at the next (double) dose level (Cohort 2) and 51.46 ng/mL at the highest (x4 of the lowest dose) dose level (Cohort 3).

The exploration of thermogenesis induction by RZL-012 in humans was successful. A raise in temperature at the injection site was mostly evident in cohort 3 (the highest dose) at Day 14 or Day 21 following injection in RZL-012 treated subjects only.

Magnetic Resonance Imaging (MRI) results demonstrated a decrease over time in Subcutaneous Mass Fat (SFM) ratio (injected/non-injected side) vs baseline in most RZL-012 treated subjects of Cohort 3. This reduction was not statistically significant. Biopsy did not yield enough tissue (because punch biopsy did not penetrate deep enough to reach the remodeled tissue) and therefore it was not possible to demonstrate changes in the adipose tissue.

Raziel concludes that the potential risk-benefit balance for RZL-012 is favorable, and it is likely that higher doses of RZL-012 will generate better results.

1.2.4.1.2. Protocol No. RZL-012-P2aUS-001.4 Status: Completed

An additional clinical trial was a double blind, randomized, placebo controlled, dose escalation Phase 2a study, conducted under IND 133324 to evaluate the safety and thermogenesis-induction of RZL-012 in overweight and obese subjects.

The primary objective of the study was the evaluation of the overall safety and preliminary efficacy of RZL-012 after subcutaneous injection. The primary endpoint for efficacy was a significant thermogenic effect, apparent at least 28 days after injection, at the injected site compared with the contra-lateral, non-injected site.

The secondary objective was the determination of RZL-012 pharmacodynamics and pharmacokinetics. The secondary efficacy endpoints included the following:

[figure not shown]
- 1. Duration of the thermogenic effect, defined as a net-delta ≥ 1 .
- 2. Local reduction in fat mass as determined by MRI.

- 3. Clinical laboratory changes from baseline
- 4. Establishing the pharmacokinetic profile for RZL-012.
- 5. Anthropometric changes from baseline
- 6. Elucidation of the histological changes that may account for the thermogenic effect by biopsy of the injection site.
- 7. Change from baseline in inflammatory markers and cytokines.

The study was composed of 4 cohorts. Each cohort was designed to enroll 8 subjects (6 active and 2 control). In Cohort 3, 3 subjects were injected with control vehicle and not 2 as planned due to subject's dropout. The overall number of subjects in the study was 33.

Subjects received a single treatment at multiple sites (8-36) of injection diagonally (45°) to the skin surface at 5 cm lateral to the umbilicus lateral wall. The distance between injected sites was 2 cm in cohorts 1-3 and 1cm in Cohort 4 as seen in Figure 2.

Figure 2: Injection Sites for Phase 2A Study

RZL-012-P2aUS-001.4 Study Results:

In the current study, in which significantly higher doses were tested (up to 180 mg), RZL-012 was found to be safe in all cohorts. There were no clinically significant changes in vital signs, ECG and all blood laboratory parameter. The most commonly reported AEs for which there seems to be a causal relationship to active treatment, due to the higher incidence in the active treatment groups compared to the placebo groups, were injection site pain and injection site edema. Most AEs were transient. There was only a single case in the highest injected dose, Cohort 4, where erythema and edema were still observed up to Day 140.

The only systemic effect found due to the subcutaneous injection of RZL-012, was elevation in d-dimer values at the highest injected dose, 180 mg. However, this increase was transient, up to 3 days after injection, and non-clinically significant.

Biopsies taken from two injection sites revealed no damage to the skin 56 days following RZL-012 injection. Based on the histology results, the process that seemed to be dominant is fat

necrosis and infiltration of macrophages into the necrotic fat tissue that resulted in a replacement of the local fat tissue by fibrotic tissue.

A decrease from baseline in SFM ratio (injected/non-injected side), as assessed by MRI, was noted in RZL-012 treated subjects of Cohorts 2-4 at all study time points. In addition, a dose dependent response was evident and statistically significant differences in SFM were found in RZL-012 treatment groups vs. Placebo. Among Cohort 4 subjects who were monitored until 168 days post injection, a clear reduction in SFM was noticed (-14.32%). Cohort 4 subjects demonstrated the largest reduction in SFM at Day 56 (-18.10%).

There were no major changes over time and no specific trend to suggest a dose correlation response in any of the parameters of lipid profile (TC, TG, LDL, HDL, and FFA) and fasting glucose.

The PK profile of RZL-012 demonstrated dose proportionality. The maximal plasma concentration of RZL-012 was less than 0.5 μ g/mL (500 ng/mL) in all subjects and T_{max} was obtained at about 2 hours following injection.

No significant decrease in BMI or in subjects' weight values was evident in all cohorts, compared to vehicle injected subjects. There was no consistent pattern to suggest an association between inflammation markers and cytokines levels. Therefore, the inflammation reaction due to macrophage infiltration into the necrotic tissue seems to be local and without any systemic effect.

Raziel concludes that the risk benefit profile of RZL-012 as seen in clinical trials to date, is in favor of RZL-012. RZL-012 may be useful in treating conditions in which removal of excess fat is desired such as excess in submental fat

1.2.4.1.3. Protocol No. RZL-012-FD-P2aUS-001.7 Status: ongoing

An additional ongoing clinical trial is an open label Phase 2a study conducted under IND 135762 to evaluate the safety and efficacy of RZL-012 for the treatment of women with lipedema involving substantial fat above the knee or of women and men with nodular Dercum's disease (DD).

The Primary objective is to evaluate the overall safety of RZL-012 following injection into the subcutaneous fat in patients with lipedema or DD.

The secondary objective is to evaluate local fat reduction, its extent, duration and tissue associated changes, in response to RZL-012 treatment, utilizing minimal invasive means (ultrasound) following subcutaneous injection of RZL-012 into fatty tissue below the skin.

[figure not shown]
The study is composed of 2 cohorts where the 1st cohort is comprised of 6 subjects with Dercum's disease and the 2nd cohort is comprised of subjects with lipedema subjects having substantial fat above the knee.

1st Cohort Dercum's disease:

Several lipomas were injected per subject. Dosing was calculated according to the size of the nodule (diameter) reaching a maximal dose of 40mg per subject

Subjects received a single treatment in multiple sites (2-8 cm lipoma size) of injection according to the design in Figure 3.

Figure 3: Injections Diagram According to Lipomas Size

2nd cohort lipedema subjects with substantial fat above the knee:

The first 3 subjects received 30 mg RZL-012 in 6 injections (0.1 mL each) in one leg followed by 30 mg RZL-012 (6 injections, 0.1 mL each) in the second leg adding up to 12 injections of 60 mg RZL-012 (1/4th the NOAEL based on Human Equivalent Dose (HED) from GLP toxicology study).

The last 3 subjects received 40 mg RZL-012 in 8 injections (0.1 mL each) in one leg followed by 40 mg RZL-012 (8 injections, 0.1 mL each) in the second leg adding up to 16 injections of 80 mg RZL-012 (1/3rd the NOAEL based on HED from GLP toxicology study), see Figure 4.

Figure 4: Injection Scheme Lipedema Subjects

12 injections of RZL-012 16 injections of RZL-012

RZL-012-FD-P2aUS-001.7 Interim Study results:

As of April 2019, all 12 subjects from both cohorts were recruited and injected with study drug.

Results for lipedema subjects are still pending.

Below are the interim results of 5 subjects with Dercum's disease. A total of 18 lipomas were injected with RZL-012 and followed up for 56 days for lipoma size changes and pain scores.

2. PURPOSE AND STUDY OBJECTIVES

2.1. PURPOSE

A single blind, randomized, placebo-controlled, Phase 2a, 2-cohort study for the evaluation of safety and efficacy of RZL-012 for submental fat reduction in healthy volunteers.

2.2. STUDY OBJECTIVES

2.2.1. Primary

To evaluate the safety of RZL-012 subcutaneous injections in the submental area, relative to placebo, as assessed by spontaneous adverse event reports and post injection evaluation of subjects by treating physician.

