6.1.14. Adverse Events

[figure not shown]
The information obtained via subjects questioning through the study visits, review of subject's compliance record, evaluation of skin irritancy, vital signs measurements, and by any other means will be evaluated in light of baseline medical data and thus provide the basis for adverse events identification and grading.

Twelve (12) subjects from cohort 1 (8 active and 4 placebo) will be injected with a maximal dose of 120 mg/subject or with up to 2.4 mL of vehicle. If no serious safety concerns will be noted within 28 days of follow-up post-dose of subjects from cohort 1, the study will proceed to the additional 16 subjects of cohort 2 that are designated to be injected with a maximal dose of 240 mg/subject for active treatment or up to 4.8 mL vehicle in at least 4 placebo subjects that will be randomized

The AEs reported during the trial will be graded (see Section 9), documented, and assessed in light of their clinical significance and relation to investigational product. Specifically, the tolerability and assessment of the AEs related to skin condition and injection procedure will be monitored among RZL-012 vs. placebo treated subjects: bruising, pain, induration erythema, and swelling/edema.

Erythema and Edema will be assessed according to Draize Score, as described in Section 6.1.7.

Pain will be assessed by using Numeric Rating Scale (NRS). NRS is an 11-point scale for patient self-reporting of pain, where 0 is no pain, rate 1-3 is mild pain, rate 4-6 is moderate pain and rate of 7-10 is severe pain, where 10 is worst pain imaginable.

Induration will be assessed by palpation of submental fat area.

Bruising will be assessed by visual inspection.

Individual 4-point grading scales were implemented to provide greater specificity in the characterization of bruising and induration (4).

Table 3: Grading scales of bruising and induration

Grade	Bruising	Induration
0	No Bruising	No Induration
1	Bruising associated with 1–3	Induration associated with at
	needle insertion points	least approximately 30% of
		the treatment area
2	Bruising spreading beyond 4	Induration associated with
	or more individual needle	greater than approximately
	insertion points but contained	30% to at least 60% of the
	within the treatment area	treatment area
3	Bruising covering the entire	Induration covering the entire
	treatment area but contained	treatment area but contained
	within it	within it

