6.1.15.1. Evaluation of Primary Endpoints

6.1.15.1.1. Safety and Tolerability Monitoring

For determination of the study's primary end point, evaluation of safety and tolerability will be conducted according to definitions and guidelines below.

Safety and tolerability will be assessed by the study medical staff (e.g., PI, site coordinator, and study nurse) and the study subjects on the basis of the following:

- 1. AEs related to skin condition and injection procedure, general AEs and SAEs, including severity, relation to study treatment and classification by whether or not these events comprise intolerable side effects.
- 2. Physical exams, Draize score and vital signs measurements.
- 3. Subjects questioning full medical history during screening, routine AE reporting.

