6.1.15.5. Questioning of Study Subjects

Questioning of study subjects during site visits and any unscheduled conversations (e.g., by phone) with site staff will be fully documented in subject file. Whenever possible, subject questioning should include, but not be limited to, inquiring information regarding occurrence and severity of AEs, treatment tolerability and compliance to future scheduled procedures and visits.

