6.2.2. Study Randomization

Subjects will be randomized to each study group, i.e., investigational therapy or control, according to a predefined randomization scheme in a ratio of 2:1 (active:placebo) among the

2 clinical sites and per each study cohort. The investigational therapy group will be treated with RZL-012 and the control group will be treated with the same formulation (vehicle) as with RZL-012, absent active medication.

Assignment to study group will be disclosed only after subject eligibility is confirmed and immediately before treatment initiation. The investigator and clinical staff will be unmasked and will be responsible to fill the syringes for injection. The subject will be blinded and will not know whether he is injected with active or placebo treatment.

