10.2. STUDY ENDPOINTS

10.2.1. Primary Safety Endpoints

Skin AEs will be evaluated for their frequency, severity and duration. Specifically, the assessment of the following AEs will be monitored among RZL-012 vs. placebo treated subjects: bruising, pain, induration, erythema, and swelling/edema.

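### Adverse events that are not graded on a scale are found by unscripted questioning from staff who know the arm, while the primary objective speaks of spontaneous reports; one fixed question would remove the difference

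*Combined protocol and SAP*

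**What the plan says.** Section 2.2.1, and the synopsis in the same terms, sets the primary objective as safety relative to placebo, "as assessed by spontaneous adverse event reports and post injection evaluation of subjects by treating physician". That names two sources: what subjects volunteer, and what the treating physician finds.

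Section 6 works differently. Section 6.1.14 lists the basis for identifying and grading AEs, beginning "The information obtained via subjects questioning through the study visits, review of subject's compliance record, evaluation of skin irritancy, vital signs measurements", and then adds any other means. Section 6.1.15.5 covers questioning at site visits and in unscheduled conversations: "Whenever possible, subject questioning should include, but not be limited to, inquiring information regarding occurrence and severity of AEs". It gives no script, recall period or order relative to the examination.

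On who asks, Section 6.1.15.1.1 states: "Safety and tolerability will be assessed by the study medical staff (e.g., PI, site coordinator, and study nurse) and the study subjects". Section 6.2.2 states: "The investigator and clinical staff will be unmasked". Only the subject is blinded.

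On what is counted, Section 10.2.1 defines the primary safety endpoint by how often local skin reactions occur, how severe they are and how long they last: "Specifically, the assessment of the following AEs will be monitored among RZL-012 vs. placebo treated subjects: bruising, pain, induration, erythema, and swelling/edema". Section 6.1.15.1.1 also brings general AEs into the primary evaluation, and Section 10.2.3 lists overall AE incidence for RZL-012 against placebo.

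**The concern.** An event that a subject volunteers and an event that comes out only on questioning are found by different processes, and the second usually yields more events. The objective names the first and the procedures use the second. If every subject is asked the same thing in the same way, the difference only changes the level of reporting in both arms. If staff who know the assignment ask active subjects more closely, the result is a difference between arms that looks like a drug effect. If they ask active subjects less closely, a real effect can be hidden.

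The safety comparison with placebo is the primary question of the trial, and Section 3.3.1 sends the Cohort 1 safety and tolerability data to the DSMB for the decision on the next cohort. Section 11.3 makes the trial forms themselves the source for answers to questioning, so no separate record would show how the questions were put.

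**Working it through.** The plan gives no figure to reproduce on this point: no AE rate, detection rate or power. The check is therefore mainly a comparison of sections.

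**1. Which events depend on questioning?**

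| Event type | How it is found | Exposed to uneven probing? |
|---|---|---|
| Erythema, edema | Draize score, all subjects, scheduled visits (6.1.7, 6.1.14) | Presence at a visit: no |
| Bruising, induration | Inspection and palpation, Table 3 grades, scheduled visits (6.1.14) | Presence at a visit: no |
| Pain | 11-point scale, rated by the blinded subject (6.1.14) | Largely no |
| Ungraded AEs, for example itching | Questioning (6.1.14, 6.1.15.5, 11.3) | Yes |
| Onset and end dates between visits | Subject's account (dates required by 6.1.14 and 9.5.1) | Yes |

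Itching is anticipated in Section 7.1 and recorded through questioning under Section 11.3, but it appears on none of the grading scales.

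**2. How much falls between visits?** Table 4 and Appendix I place post-injection AE assessments on Days 0, 1, 7, 14, 28, 56 and 84. The gaps are 1, 6, 7, 14, 28 and 28 days. Duration is part of the primary endpoint. From Day 14 on, an end date can lie anywhere in a gap of 14 or 28 days, and only the subject's account can place it.

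**3. How large could the effect on ungraded AEs be?** This is an illustration only. Observed rate = true rate × probability of detection in that arm. Assume the same true rate *p* in both arms, detection of 0.9 on active and 0.5 to 0.7 on placebo. The false difference is *p* × (0.9 − detection on placebo):

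- *p* = 0.2: 0.2 × 0.2 = 4 points, to 0.2 × 0.4 = 8 points
- *p* = 0.3: 0.3 × 0.2 = 6 points, to 0.3 × 0.4 = 12 points
- *p* = 0.5: 0.5 × 0.2 = 10 points, to 0.5 × 0.4 = 20 points

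With equal detection the difference is 0. With probing the other way round the sign reverses.

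**4. What is that in subjects?** Table 2 gives 4 placebo subjects in Cohort 1 and at least 4 in Cohort 2, so at least 8 of 28 overall and then 20 on active. At *p* = 0.3 the expected numbers with a recorded event are 20 × 0.27 = 5.4 on active, and 8 × 0.15 = 1.2 to 8 × 0.21 = 1.68 on placebo. With 0.9 detection, placebo would show 8 × 0.27 = 2.16. The shortfall is 0.48 to 0.96 of a subject. One placebo subject is 1/8 = 12.5 points pooled and 1/4 = 25 points in Cohort 1, so a single unasked question can move the table visibly.

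**The case against.** The strongest reply is that the primary endpoint is not a count of spontaneous reports. Sections 4.1 and 10.2.1 name five local reactions, assessed in both arms on the same days with set instruments. This stands, and it limits the point. A reader might infer that the whole primary comparison depends on who is asked and how hard; the documents do not support that. What remains for the five reactions is unmasked scoring, which is a separate issue, and the dating of onset and resolution between visits.

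A reader might also infer that asking about AEs is optional at visits, so that some subjects contribute elicited events and others only volunteered ones. That does not stand either. Section 9.2 requires AEs to be documented at every visit, and Table 4 and Appendix I schedule the assessment for everyone. The whenever-possible qualifier in Section 6.1.15.5 governs the content of questioning and also covers unscheduled telephone contacts. An illustration in which one arm is always questioned and the other never is would therefore describe a different trial.

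Further, the AE definition in Section 9.1.1 does not depend on how an event comes to light, Section 9.5.1 requires all AEs to be recorded, and the objective's second source, the physician's evaluation, takes in what is found on examination. So the objective's wording alone excludes little. Section 10.5.1 already presents injection-related AEs and Draize scores in their own tables, by visit, cohort and treatment.

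None of this sets how the question is put. Documenting AEs at each visit does not make the enquiry the same in both arms when the person asking knows the assignment.

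**Conclusion.** The point holds for ungraded AEs and for onset and end dates between visits. For these, counts and durations can differ between arms through probing alone, and nothing in the plan standardises the probing. The mismatch between the objective and Section 6 is real but by itself only a matter of wording; the substance is unscripted questioning by unmasked staff.

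The size cannot be derived from the documents. The range of 4 to 20 points rests entirely on the assumed true rates and detection probabilities, and it should not be applied to the five graded reactions. Nothing shows that staff would in fact probe unequally. Because Section 10.5.1 makes the analysis mainly descriptive, no power or type I error figure changes. The change is worth making because it is nearly free.

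**What to change.** 1. In Section 2.2.1 and the synopsis, replace the reference to spontaneous reports with *adverse events volunteered by the subject or elicited by a standard question*, and keep the physician's evaluation as the second source.
2. In Section 6.1.15.5, require one fixed, non-leading question, read word for word to every subject in both arms at each scheduled visit before any examination. Keep the whenever-possible qualifier for unscheduled contacts only.
3. In Sections 10.5.1 and 10.5.6, state that the scheduled graded reactions are reported separately from all other AEs, each by treatment and cohort. Section 10.5.6 currently names cohort only.
4. Optional: a CRF field recording whether each AE was volunteered, elicited or found at scheduled grading. A listing would be enough, since splitting tables three ways in 28 subjects would leave near-empty cells.

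The cost is a few sentences and a line of CRF instruction, with no added visits or staff. Recorded AE rates may be slightly higher in both arms. The change does not address unmasked scoring of the Draize, bruising and induration grades.
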